An early stopping rule pending further investigation for this study will be invoked if any of the following adverse events occur:

- The rate of BSI in SBS patients in either the GLN supplementation or the placebo is an absolute 20% higher compared to the historical rate in SBS patients. The rate of catheter associated BSI is assessed monthly in all SBS patients at both CCHMC and the University of Michigan as part of the current clinical improvement process, If the rate of the BSI is higher in either group by 20% then study enrollment will be halted until further evaluation by the Data Safety Monitoring Board (DSMB).
- If two subjects develop the same grade-3 adverse event (including liver function tests, coagulation profile) related to the study medication that is irreversible upon de-escalation (does not reverse after 10 days) or upon discontinuation of the study drug
- Any subject develops a related grade-4 adverse event.

Since this is a double blind placebo control design, the data will only be unmasked by the research pharmacy at the request of the DSMB, if any of the above events occur. The statistician on the DSMB will evaluate the data. The unmasked data will not be revealed to the investigators unless the DSMB requests that the study be terminated.

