## H. Study Procedures

### **Randomization and study groups**

[figure not shown]
At the baseline visit, SBS subjects will be block randomized in a 1:1 scheme by site and strata (i.e the presence or absence of **colon in continuity**) to receive either L-GLN powder or isonitrogenous, isocaloric placebo [L-alanine (ALA)]. Randomization will be done by the Cincinnati Children's Hospital Medical Center research pharmacist who will not be blinded. Distribution will be done by the site study personnel. The subjects, site investigators and study personnel at all sites will be blinded to the randomization. Since patients will be on breast milk or Elemental formula (Elecare® being the preferred elemental formula at both institutions; however use of other elemental formula does not exclude the patient from the study), the randomization process will take into account whether breast milk or formula is been consumed by the infant. The research pharmacist will make decisions regarding randomization based on the use of formula versus breast milk to ensure adequate distribution within groups.

**Glutamine group:** Infants randomized to the GLN group will receive L-GLN administered enterally at a dose of 0.6g/kg body weight/day (0.3g/kg/dose) in 2 divided daily doses for 6 months (figure 2). GLN will be dissolved in water, breast milk or formula and administered to the subject orally or through their enterostomy tube approximately every 12 hours (twice a day). This can be administered as a bolus or a continuous infusion lasting a maximum of 2 hours. We will use Nutrestore™ (Emmaus Medical, Inc.), a commercially available, FDA approved pure L-GLN product in the study. In the event that this is not available we will use commercially available 100% USP grade L-GLN. The minimal volume L-GLN will be dissolved in at least 10 ml of water, breastmilk or formula.

**Placebo group:** Infants in the placebo group will receive ALA at a dose of 0.6g/kg body weight/day in 2 divided doses (0.3g/kg/day twice a day), exactly as outlined above for the GLN group.

ALA is a non-essential amino acid and will be used as the placebo in this study because it is a nutritional supplement without any known impact on gastrointestinal permeability or local effect on the mucosa or infections. It will balance out the administration of an amino acid (L-GLN) to the study population.

Figure 2: Study design

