## **XI. Assessment of Safety**

A DSMB will monitor the study for the occurrence of adverse events (both serious and otherwise). A significant increase in the rate of adverse events would be cause for concern for the safety of participants in the study. Information on adverse events will be presented in several ways: (1) listings of serious adverse events with accompanying narrative summary by the PI; (2) summaries of adverse events by body system and type of event. This information will be presented to the DSMB.

Interim monitoring reports for the DSMB will include, but will not be limited to, such tabulations as:

1. Frequency of BSI and hospitalization
2. coagulation studies
3. liver profiles
4. renal profiles
5. Frequency of adverse events

The DSMB will meet at the start of the study, then after 5 patients have received treatment. Subsequent meetings will be at the discretion of the chair given the expected speed of recruitment and study medication administration.

The DSMB chair (or designee) will be asked to review SAE reports within 48 hours after initial receipt of the information by the investigator(s), to review the PIs assignment of SAEs as related or unrelated to treatment, to confirm the grading of any toxicities. This will also be reported to the site IRB and the study sponsor.

A safety analysis will be performed after approximately 5 patients have received treatment or, if enrollment begins slowly, 12 months after the first patient is enrolled. Safety data will be shared with the Data and Safety Monitoring Board (DSMB). An investigator in this study will not be a member of the DSMB. Members of the DSMB will receive safety data approximately every 6 months for review or more frequently if requested by the chair. Safety assessments will consist of vital signs, AEs, and laboratory evaluations. A cumulative listing of patient withdrawals, dose adjustments, and serious adverse events (SAEs) will also be reviewed. DSMB members will be notified of all SAEs reported expeditiously to regulatory authorities.

[name], Division of Gastroenterology, will act as the chair of the DSMB. There will be 2 other members appointed to the DSMB: a statistician ([name]) and a neonatologist ([name]), who are not involved in the conduct of the study. [name] will serve as the safety officer for this study. The safety officer is not a member of the DSMB and he is an expert on glutamine metabolism and use in children with chronic and persistent diarrhea.

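### The BSI stopping rule needs rates by arm that the plan does not supply before the rule fires, and its threshold, event and historical comparator are not defined

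*Combined protocol and SAP*

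**What the plan says.** Section IX.D (Stopping Rules) gives three triggers. The first concerns BSI, which is also the primary endpoint: "The rate of BSI in SBS patients in either the GLN supplementation or the placebo is an absolute 20% higher compared to the historical rate". The same bullet then says "The rate of catheter associated BSI is assessed monthly in all SBS patients at both CCHMC and the University of Michigan", and it ends with the consequence: "If the rate of the BSI is higher in either group by 20% then study enrollment will be halted until further evaluation" by the DSMB. A closing paragraph covers masking: "the data will only be unmasked by the research pharmacy at the request of the DSMB, if any of the above events occur".

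Section XI (Assessment of Safety) describes what the DSMB receives. It begins "Interim monitoring reports for the DSMB will include, but will not be limited to, such tabulations as" and the first item is "Frequency of BSI and hospitalization", with no mention of arm or coded arm. The adverse-event summaries are by body system and event type. On timing, the DSMB meets at the start and after 5 treated patients, and "Members of the DSMB will receive safety data approximately every 6 months for review".

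Three other places bear on the point:

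- Randomization and study groups (section IX.H) names a "Medical Center research pharmacist who will not be blinded" but gives nobody the task of tabulating BSI by arm.
- Recording of Adverse Events (section XII) takes BSI out of routine adverse-event reporting. It readmits catheter-associated BSI only above a 20% threshold, worded in yet another way and set against the centre's standard.
- Section X (Assessment of Efficacy) says that the BSI definition separates catheter-related BSI from other BSI.

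**The concern.** There are two separate faults.

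**Route of the data.** The BSI trigger is the only one of the three that depends on a rate in each arm. The grade-3 and grade-4 triggers count events in individual infants and can fire on masked data. For BSI, someone must see the arms, at least under codes, before the rule can be judged. The plan permits unmasking only once a trigger has occurred and provides no other route. Followed literally, the DSMB would see an excess confined to one arm only in pooled counts, where it is diluted.

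**Definition of the trigger.** Four things are open: whether 20% is absolute or relative, whether the event is any BSI or only catheter-associated BSI, what the historical rate is, and in what unit. The same counts could then halt enrolment on one reading and not on another.

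At stake is whether an arm-specific excess of the primary endpoint, in infants, would be recognised while a pause in enrolment could still matter.

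**Working it through.** **What there is to reproduce.** The plan gives no trigger count and no operating characteristic for this rule. The Sample size section does give planning rates of 75% and 30% with 16 completers per arm. Its stated power of at least 85% (Fisher's exact test, one-sided 10%) reproduces as 85.7% and is not affected by this point.

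**Dilution.** Let the historical risk be h, with one arm at h + 20 points and the other at h. The pooled excess is ((h + 0.20) + h)/2 − h = 0.10, half the true excess. If the other arm lies 20 points below h, the pooled excess is 0. With arms at 95% and 30% against h = 75%, the pooled rate is (95 + 30)/2 = 62.5%, which is 12.5 points below historical.

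**Assumptions for the probabilities.** One look; rate means the proportion of infants with at least one BSI; complete 6-month follow-up. The historical risk is not stated, so h is taken as 75%, 50% and 30% (the two planning rates and a value between them). The trigger is the smallest count r with r/n at or above h + 0.20 (absolute) or 1.2h (relative).

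**Formulas.**
- Chance crossing in one arm: q = P(X ≥ r), X ~ Binomial(n, h).
- At least one of two arms: 1 − (1 − q)².
- Detection in the affected arm: P(X ≥ r), X ~ Binomial(n, h + 0.20).
- Pooled detection: the sum of the two arms' binomials reaching the same absolute threshold among 2n infants.

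**Detection when one arm is truly 20 points worse (absolute reading).**

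| n per arm | h | Count needed in arm | Arm table crosses | Pooled count needed | Pooled table crosses |
|---|---|---|---|---|---|
| 8 | 75% | 8/8 | 66.3% | 16/16 | 6.6% |
| 8 | 50% | 6/8 | 55.2% | 12/16 | 16.1% |
| 8 | 30% | 4/8 | 63.7% | 8/16 | 28.0% |
| 16 | 75% | 16/16 | 44.0% | 31/32 | 3.2% |
| 16 | 50% | 12/16 | 45.0% | 23/32 | 11.0% |
| 16 | 30% | 8/16 | 59.8% | 16/32 | 16.0% |

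**Chance crossing when neither arm has an excess.**

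| n per arm | h | Absolute: count, q, either arm | Relative: count, either arm | Pooled, absolute |
|---|---|---|---|---|
| 8 | 75% | 8/8, 0.1001, 19.0% | 8/8, 19.0% | 1.0% |
| 8 | 50% | 6/8, 0.1445, 26.8% | 5/8, 59.5% | 3.8% |
| 8 | 30% | 4/8, 0.1941, 35.1% | 3/8, 69.6% | 7.4% |
| 16 | 75% | 16/16, 0.0100, 2.0% | 15/16, 12.3% | 0.1% |
| 16 | 50% | 12/16, 0.0384, 7.5% | 10/16, 40.3% | 1.0% |
| 16 | 30% | 8/16, 0.0744, 14.3% | 6/16, 56.5% | 1.4% |

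Example: for n = 8 and h = 50%, 1 − (1 − 0.1445)² = 0.268. In that case 5/8 crosses on the relative reading and does not on the absolute one.

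**First review.** At about 5 treated infants, take 3 per arm. On the absolute reading, at least one arm crosses by chance with probability 67, 23 or 39% for h = 75, 50 or 30%.

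**At or strictly above.** If the threshold must be exceeded rather than reached, only the 30% absolute figures change. Detection becomes 36.3% against 13.7% pooled (n = 8) and 40.2% against 8.7% (n = 16). Chance crossing in either arm becomes 11.3% and 5.1%.

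**Other unit.** The only catheter-sepsis rate for short bowel syndrome in the documents is 7.8 per 1000 catheter days (Background). On that scale an absolute 20% has no direct meaning. A relative 20% could be computed: with 18 infants, 180 days each and a catheter in place throughout, 7.8/1000 × 18 × 180 = 25.3 events are expected per arm. Then 1.2 × 25.3 = 30.3, so 31 events trigger.

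**The case against.** The case on the other side is partly right.

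- **The route argument rests on silence.** No section says that the DSMB sees only pooled data. The list of tabulations is expressly open, A/B codes need not count as unmasking, and a rule written for either group implies that somebody tabulates by group. This stands to the extent that coded tables are allowed. It does not supply them: no one is assigned the task, and the one sentence on unmasking makes it conditional on a trigger.
- **The later 20% is probably shorthand for the absolute one.** That is the natural reading, so the relative-reading figures should carry less weight. Settling it would still leave the event, unit, comparator value and period open.
- **The adverse-event threshold governs recording, not stopping.** True. It is a related wording to reconcile, not a contradiction inside the stopping rule.
- **The probabilities rest on a scale and historical risks that the plan does not give.** True. The 75% and 30% are planning rates for the arms, and nothing says that the DSMB would apply the threshold to a pooled table. The figures illustrate the mechanism and do not predict this trial.
- **Arm-level tables at the first review would often cross by chance.** True, as the figures for 3 per arm show, and follow-up would then be incomplete as well.
- **The consequence is limited.** The BSI trigger pauses enrolment pending DSMB evaluation; it does not end the trial. This also stands.

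**Conclusion.** The concern holds on both counts. As written, the BSI trigger cannot be evaluated from the data that the plan provides to the DSMB. Even with arm-level data it could not be computed without choosing an event, a unit and a historical value.

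Under the stated assumptions (one look, proportion scale, complete follow-up, historical risk between 30% and 75%), reliance on pooled counts cuts the chance of seeing a 20-point excess in one arm from 55–66% to 7–28% at 8 per arm. At 16 per arm it falls from 44–60% to 3–16%. The wording of the 20% moves the chance-crossing probability by nothing at 75% and 8 per arm, but from 27% to 59% at 50%. The missing historical rate thus determines how much the ambiguity matters. Repeated looks would raise all the chance-crossing figures.

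The primary analysis and the power statement are untouched. This should be fixed, but it does not invalidate the design.

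**What to change.** 1. **Data route.** State in the Stopping Rules and Assessment of Safety sections that the DSMB statistician receives coded A/B tables of BSI episodes and of infants with at least one BSI at every scheduled review, from the first. Full unmasking stays at the DSMB's request.
2. **Definition.** Reconcile the Stopping Rules, Assessment of Safety and Recording of Adverse Events sections to one BSI event, one unit, one historical comparator with its value and time window, and one reading of the 20%. Say whether the threshold must be reached or exceeded. Which threshold and which passage govern is for the sponsor and the DSMB to decide.
3. **Operating characteristics.** State the resulting probability of crossing by chance at the planned reviews, including the one at about 5 treated patients, so that the DSMB can weigh an early crossing.

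**Cost.** Small: protocol wording and one coded table per review. The DSMB already has a statistician, the research pharmacist is already unblinded, and BSI dates are already collected. Catheter-days are not among the listed data items, so a catheter-day rate would need one more item. The downsides are one partly unblinded DSMB member and more false pauses at early reviews.

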#### E. Monitoring for toxicity due to GLN

Potential toxicity will be assessed by analyzing clinical and laboratory parameters using the following PN labs (Complete blood count, complete metabolic profile (Renal, Calcium, Phosphorus, Magnesium, Liver panel, Total Protein, Albumin) monthly. Additional blood samples will be done in accordance with current institutional standards for monitoring chronic PN use in infants. Plasma GLN levels will be obtained at baseline and at 6 months.

#### F. Evaluating compliance

All of the subjects will be instructed to bring to the monthly visits, the containers containing the supplement supplied at the previous visit. The study team will count the remaining bags left over. We will also evaluate the diary provided to the families. Compliance will be evaluated based on the diary and the number of returned containers. Families are expected to be 90% compliant. If the child/family is less than 90% compliant, the family will receive additional counseling to identify reasons and how to attain this level of compliance. Children will remain in the study as long as they receive at least 70% of the expected amount for 3 consecutive months. The level of compliance on enteral GLN effect will be included in the analysis. Children who receive less than 70% or more than 120% of the prescribed glutamine or placebo will be considered to be non-compliant. The reason for non-compliance will be documented and included in the final analysis. Average intake/day of glutamine by the patients will be included in the analysis including the response based on dose received.

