4. The family will be instructed on how to administer GLN and placebo. During the baseline visit, the initial teaching will be done and they will be provided with the premeasured powder. The dose (0.6g/kg/d (0.3g/kg/dose) of GLN or ALA) will be measured out in the research pharmacy based on the weight of the child at the visit into individual packets. Children hospitalized during the study will receive GLN or ALA from the research pharmacy delivered to the patient's bedside to be administered by nursing staff. At subsequent visits (except visit on day 180), this teaching will be repeated as the dose to be administered will change based on the weight of the child. The family will also be given a weekly drug diary to complete in between visits. They will return the drug diary to the study staff during subsequent visits.
5. During the initial visit, stool will be collected into sterile containers and stored at -80°F until analysis for sIgA and bacterial composition evaluation. It is anticipated that the majority of stool will be collected in clinic during the study visit. If stool is collected in clinic, the stool will be stored immediately in the -80°F freezer without any need for DNA stabilizer.

If stool is not collected during this visit, families will be instructed on how to collect stool for evaluation into a sterile container. They will put this in a storage bag and kept cold until picked up by the home health team or delivered to the research team.

Patients already enrolled will be provided with a sterile container with instructions to collect stool and bring in to the clinic visit for storage and analysis. The family will be asked to collect stool 24-48 hours before their clinic visit and put the stool in a sterile container which will be supplied to them by the study team. They will put this in a storage bag and keep cold. They will bring the sample to the clinic visit. RNAlater may be used with samples when samples are unable to be obtained within 24 hours of the clinic visit.

**Stool sIgA analysis:** sIgA will be determined by ELISA as described.

**During baseline visit and visit on day 180** the following additional procedures will be done: Extra 2 ml of blood will be collected for plasma glutamine, proinflammatory cytokines analysis, flagellin and LPS specific IgG levels.

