**During a BSI** the following procedure will be done: stool collection for bacterial analysis and sIgA measurement. Extra 2 ml of blood will be collected for flagellin and LPS specific IgG levels. The blood will be obtained as soon as possible when the patient is being investigated for a suspected CA-BSI. In the event that the episode does not meet the criteria for a CA-BSI the samples will not be evaluated.

All bacterial isolates obtained during the study from patients will be saved at their respective institutions (CCHMC and University of Michigan) until the end of the study in the event further work with them is required.

**Plasma glutamine analysis:** Plasma GLN will be performed using quantitative ion exchange chromatography.

**Proinflammatory cytokine evaluation:** Analysis will be performed utilizing Luminex xMAP technology (Austin TX) as previously described.

**Measurement of Flagellin and Lipopolysaccharide- specific Immunoglobulin G level:** This will be done using enzyme-linked immunosorbent assay (ELISA) as previously described.

**Safety evaluation:** The study coordinator will contact the family by phone to assess for the development of any serious adverse events on days 15(±7 days), 45 (±7 days), 75 (±7 days), 105 (±7 days), 135 (±7 days) and 165 (±7 days). There will be a 7 day grace period before and after the desired date of safety evaluation phone calls. The phone interview will assess safety and evaluate for any symptoms suggestive of adverse side effects related to L-GLN. If hospitalized, the safety evaluation will occur with the primary caregiver (bedside nurse or parent).

**Additional safety precautions:** If while enrolled in the study the patient develops multiorgan failure or requires vasopressors, the study drug will not be administered.

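### The compliance score names only the family diary and returned packets, so infants dosed by nurses in hospital may be under-counted and the dose-response analysis biased

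*Combined protocol and SAP*

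**What the plan says.** Section IX.F sets the scoring rule: "Compliance will be evaluated based on the diary and the number of returned containers". The containers are those supplied at the previous visit, and "The study team will count the remaining bags left over". The diary is kept by the family: "The family will also be given a weekly drug diary to complete in between visits" (IX.H, item 4).

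The same item 4 sets up a second supply route: "Children hospitalized during the study will receive GLN or ALA from the research pharmacy", delivered to the "bedside to be administered by nursing staff".

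Two rules in IX.F use a 70% limit. One concerns staying in the study: "Children will remain in the study as long as they receive at least 70% of the expected amount for 3 consecutive months". The other is a label: "Children who receive less than 70% or more than 120% of the prescribed glutamine or placebo will be considered to be non-compliant". Below 90%, the family is counselled. IX.F also says that the level of compliance, the reason for non-compliance, average daily intake and response by dose received will enter the analysis. Item 6 of the secondary outcomes in section XIII plans a dose-effect analysis on compliance.

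Under Additional safety precautions in IX.H, if a patient "develops multiorgan failure or requires vasopressors, the study drug will not be administered".

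The withdrawal list in IX.B has no compliance percentage. IX.C keeps data already collected from withdrawn infants under intent to treat.

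**The concern.** The score is built from two family-side sources, while doses in hospital come from a different stock and are given by someone else. Packets are measured out at the preceding visit, so those meant for days later spent in hospital come back as leftover bags. Unless a parent happens to enter nurse-given doses in the diary, a fully dosed inpatient looks like one who missed doses. If the parent does enter them, the diary and the bag count disagree, and no rule says which prevails.

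The error would not fall at random. The Background names hospital stays for BSI as a driver of cost, BSI is the primary outcome, and readmissions and length of stay are secondary outcomes. Infants with BSI are therefore the ones most likely to have their dose under-recorded. A dose-response analysis on that variable could show fewer infections at higher dose even if glutamine did nothing, because infection leads to admission and admission lowers the recorded dose.

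**Working it through.** **Inputs from the documents.** Thresholds of 70% and 90% (IX.F); monthly visits and a three-month retention window (IX.H, IX.F); 16 completers per arm and BSI rates of 75% versus 30% (Sample size); 7.8 catheter-sepsis episodes per 1000 catheter days in infants with short bowel syndrome (Background).

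**Not in the documents.** Length of stay per admission, so a range is shown. The share of home doses taken is varied; 90% is the level IX.F expects of families.

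**The plan's own figure.** The plan gives none on this point. Its main design figure, at least 85% power with 16 per arm, reproduces at 85.7% by exact enumeration of the one-sided 10% Fisher test. The point here does not depend on it.

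**Formulas.** Let D be days in the window, h inpatient days, and c the share of home doses taken.
- Nurse-given doses earn no credit, denominator unchanged: score = c × (D − h) / D.
- All nurse-given doses credited, every inpatient dose given: score = (c × (D − h) + h) / D.

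**Inpatient days at which the no-credit score first falls below 70%.**

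| Home dosing c | 30-day window | 90-day window |
|---|---|---|
| 100% | 10 days: 20/30 = 66.7% | 28 days: 62/90 = 68.9% |
| 90% | 7 days: 0.9 × 23/30 = 69.0% | 21 days: 0.9 × 69/90 = 69.0% |
| 80% | 4 days: 0.8 × 26/30 = 69.3% | 12 days: 0.8 × 78/90 = 69.3% |

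The counselling limit is reached sooner: with perfect home dosing, 4 inpatient days in 30 score 26/30 = 86.7%, below 90%.

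**How the order reverses.** Take two infants who each receive 90% of home doses.
- Never admitted: recorded 90%, received 90%.
- 7 of 30 days in hospital: recorded 69.0%, received (0.9 × 23 + 7)/30 = 92.3%.
- 14 of 30 days in hospital: recorded 0.9 × 16/30 = 48.0%, received (0.9 × 16 + 14)/30 = 94.7%.
- 14 of 90 days in hospital: recorded 0.9 × 76/90 = 76.0%, received (0.9 × 76 + 14)/90 = 91.6%.

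The admitted infant received slightly more and is recorded as having received much less.

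**Typical burden.** At 7.8 per 1000 catheter days, with a catheter assumed throughout, an infant has 0.0078 × 180 = 1.4 episodes in 180 days. With an assumed 7 to 14 inpatient days each, that is about 10 to 20 days. With perfect home dosing the no-credit score is then 170/180 = 94% to 160/180 = 89% over the whole study. If every one of those days fell in one 90-day window, it would be 80/90 = 89% to 70/90 = 78%.

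**How few infants carry the analysis.** On the design rates, 0.30 × 16 = 4.8 glutamine infants and 0.75 × 16 = 12 placebo infants have at least one BSI. A dose-response within the glutamine arm would rest on about five infants with BSI, so a few under-recorded doses could produce a gradient.

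**The case against.** A reader might infer that the plan scores inpatient doses as missed and removes infants because they were admitted. The documents do not support that.

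- **Nothing says that inpatient doses count as missed.** Both 70% rules turn on what the child receives, and nurse-given doses are received. The diary covers the time between visits and is not limited to home days. The documents are silent, so under-counting is a risk of following the stated rule, not a stated outcome. This stands.
- **Removal is weakly supported.** The sentence is framed over three consecutive months, with no statement whether each month or the pooled period is meant. Pooled over 90 days, it takes three to four weeks in hospital at 90 to 100% home dosing, more than the typical burden worked out above. The withdrawal list has no such criterion. This stands, although the two sections still disagree.
- **The primary result is barely touched.** An infant admitted for BSI already counts as an event in the Fisher test and in time to first BSI, and data already collected are kept. This stands. What removal could cost is later data: repeat BSI, growth visits and day-180 samples.
- **Reasons for non-compliance are documented, so an admission would surface.** This helps interpretation but does not correct the number that enters the dose analysis.
- **Withheld doses are a minor part.** Developing multiorgan failure already meets a withdrawal criterion, so mainly vasopressor use remains. The expected amount is also undefined, so whether withheld doses stay in it is unknown. This stands, and a definition is still needed.

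**Conclusion.** The point holds as a likely under-count with one main consequence. Followed as written, the scoring rule uses sources that miss nurse-given doses unless parents copy them into the diary, so recorded dose may be too low in admitted infants. A single stay of 7 to 10 days is enough to take one month below 70% at 90 to 100% home dosing. Over 90 days it takes 21 to 28 inpatient days. These thresholds assume no credit for inpatient doses and an unchanged denominator.

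The exposure lies in the compliance and dose-response analyses of IX.F and section XIII, item 6, where the artefact would run in glutamine's favour: low recorded dose with more BSI. The effect on the primary comparison is small. A secondary exposure is follow-up lost after BSI if the 70% sentence were enforced as removal, which the documents leave unresolved.

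**What to change.** In IX.F:

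1. Define compliance as doses taken divided by doses due, and state the window over which each 70% rule is computed.
2. Add to the numerator the inpatient doses charted in the hospital administration record. Hospital days should not be credited automatically, because some doses are not given.
3. Take doses held under Additional safety precautions out of doses due. Average daily intake, which IX.F analyses separately, should still reflect what was actually given.
4. State which source prevails when the diary, bag count and hospital record disagree.

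Reconcile the stay-in-study sentence in IX.F with the withdrawal list in IX.B and the intent-to-treat statement in IX.C, so that it is clear whether outcome data continue to be collected from infants scored below 70%. Which participation rule applies is for the sponsor to settle.

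The cost is one CRF field filled from the hospital administration record, a few sentences of text, and a few minutes of coordinator time per admission.
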